### c. **Outcomes:**

Primary outcome:

Ease of use of ClearSight blood pressure monitoring system

(0 – 10) Ratings from patient and patients' assigned nurse during ELA

Feasibility of blood pressure monitoring (yes/no response from assigned nurse regarding patient care.

Time-to-treatment of hypotension (minutes)

Secondary outcomes: (only exploratory)

Total time in hypotension with MAP <65 mmHg

Nausea

Vomiting

Total phenylephrine, mg

Total ephedrine, mg

Total intravenous fluids, mL  
Changes in fetal heart rate category  
Presence or absence of fetal heart rate decelerations within 1 hour of initiation of ELA  
CO, CI, SV, SVV

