## III. Investigational Plan

### 1. **Study design:** Prospective randomized controlled trial

### 2. **Methods:**

a. **Size of study groups(s):** The primary outcomes are 1.) ease and feasibility of use of the ClearSight monitoring system during labor and delivery, post-epidural-labor analgesia placement; and 2.) time-to-treatment of hypotension, defined as MAP <65 mmHg for more than 1 minute. Our initial pilot sample is expected to identify the ability to use the ClearSight monitoring in the labor and delivery suite, the patient adherence to the finger cuff monitors, and the feasibility of hypotension detection at the central monitors. The pilot sample (N = 30) is not expected to demonstrate significant differences in the relation between mode of blood pressure measurement and time-to-treatment of hypotension but should yield an estimate of the potential differences for a continuance of study.

b. **Environment and Estimated timeline to sample size acquisition:** UPMC Magee performs about 7,400 ELA annually, a range of 20-30 ELA daily. Based on a meta-analysis of trials, the estimated incidence of hypotension after initiation of neuraxial analgesia during labor is approximately 19% (range: 3-35%). Our internal data that shows approximately 20-30% of patients receiving ELA require treatment with a vasopressor within the first 4 hours of ELA initiation; we will use the conservative estimate of 20%. Our internal experience with similar trials also informs our timeline: in our prior experiences with similar labor and delivery trials we have achieved a consistent approach-to-recruit ratio of about 25%. Based on our volume, ELA utilization, eligibility criteria, and rates of ELA-associated hypotension, we estimate a total of 5-8 weeks of recruitment. A total of N=30 patients will be enrolled with a predicted 20% (n=6) experiencing hypotension events of interest.

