**e. Protocol specific methods:**

Patients will be screened electronically using the electronic health record upon arrival at the Womancare birth center at UPMC Magee. Patients are eligible if they are pregnant, admitted for labor and delivery, and receiving ELA. If patients are undecided about whether they will receive ELA but are interested in the research, they may be consented and then marked as a "screen failure" if they do not receive ELA. These patients will not be randomized. Patients who receive ELA will be randomized to treatment of hypotension according to conventional monitoring (Group CM) or monitoring by HPI (Group HPI). Randomization will be 1:1 and occurs immediately after informed consent and signature for research activities. Subjects will be informed of their assignment after all research activities and data collection have been completed. Total monitoring time will be 4 hours starting from the initiation of ELA. To enable group comparisons of total time in hypotension, all participants will wear ClearSight and a Conventional Monitoring cuff; Group CM will be blinded to ClearSight output and receive standard care for the treatment of hypotensive events post-epidural-labor analgesia. Group HPI will receive treatment of hypotension according to ClearSight output and specified by the hypotension treatment protocol below.

Clinical research staff who have been trained in ClearSight will apply the device and troubleshoot any problems. Providers will be trained on the monitor, its interpretation, and output, prior to study launch and real time at the time of active study participant enrollment. This training applies only to those participants who will receive non-blinded treatment assignment

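### Two stated aims of the pilot, finger-cuff adherence and detection at the central monitors, have no listed outcome or analysis; feasibility is one nurse yes/no without a criterion

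*Combined protocol and SAP*

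**What the plan says.** Section III.2.a makes ease and feasibility of ClearSight use the first primary outcome and names what the pilot should deliver. The first item is general: "Our initial pilot sample is expected to identify the ability to use the ClearSight monitoring in the labor and delivery suite". Two specific items follow: "the patient adherence to the finger cuff monitors, and the feasibility of hypotension detection at the central monitors".

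Section III.2.c then defines the measures. Ease of use is a 0-10 score from the patient and the assigned nurse. Feasibility is "Feasibility of blood pressure monitoring (yes/no response from assigned nurse regarding patient care". No criterion says what earns a yes. The third primary outcome is time-to-treatment, and the exploratory secondary outcomes are clinical and haemodynamic.

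Three other provisions matter:

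- Support (III.2.e, Protocol specific methods): "Clinical research staff who have been trained in ClearSight will apply the device and troubleshoot any problems".
- Who wears the device (same section): "all participants will wear ClearSight and a Conventional Monitoring cuff; Group CM will be blinded to ClearSight output". The research window is 4 hours from the start of ELA.
- Exclusions (III.2.d): the list includes being unable to use ClearSight, whatever the cause, and having incomplete data.

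In III.4.b, the only primary analysis set out is the proportional hazards analysis of treatment-free time. The nurse's answer and the ease ratings fall under the general descriptive paragraph.

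**The concern.** The aims in III.2.a and the measures in III.2.c do not match. Whether patients keep the finger cuff on, and whether hypotension is picked up at the central monitors, are matters of fact about the device in use. A nurse's overall opinion and an ease score answer neither. A yes is compatible with long periods without signal.

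This matters because feasibility is the main thing the pilot can deliver. III.2.a itself says that the sample is not expected to show a difference in time-to-treatment. Wear time also affects another outcome. Total time in hypotension cannot be read without knowing how many minutes were observed, because a cuff that is off the finger records no hypotension.

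**Working it through.** **1. The plan's own figure.** III.2.b states: "A total of N=30 patients will be enrolled with a predicted 20% (n=6) experiencing hypotension events of interest". Check: 30 × 0.20 = 6. It reproduces. The plan gives no precision or power calculation for feasibility, so there is none to check.

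**2. Aims against measures.**

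| Aim in III.2.a | Outcome in III.2.c | Analysis in III.4.b |
|---|---|---|
| Ability to use ClearSight on the unit | Nurse yes/no; 0-10 ratings by patient and nurse | General descriptive paragraph only |
| Finger-cuff adherence | None | None |
| Detection at the central monitors | None | None |

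Two of the three aims have no measure. Total time in hypotension uses continuous pressure data, but it measures neither wear nor detection at a central display.

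**3. What the nurse's answer can miss.** The window is 4 × 60 = 240 minutes. As an assumption for illustration only, take a cuff that gives no signal for 180 of them: (240 − 180) / 240 = 25% valid time. Nothing in III.2.c prevents a yes for that patient.

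**4. Is the better measure available?** The stated reason for putting ClearSight on both groups is to compare total time in hypotension, so a device record is needed in both. The ELA Protocol starts data recording at T0. Valid minutes over eligible minutes can come from that record, assuming that the export marks signal loss.

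**5. The denominator.** Incomplete data can be known only after monitoring, so that exclusion can remove patients after enrolment. Suppose k of 30 patients have no usable signal and the others average a valid fraction w. With everyone counted, the mean is w × (30 − k) / 30. With the failures removed, it is w. The documents give no k. Taking 3 to 6 as an assumed range, the factor is 27/30 = 0.90 to 24/30 = 0.80. A wear-time outcome that kept those exclusions would hide the failures it is meant to show.

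**6. How much a count of central-monitor detection could show.** Allocation is 1:1, so 30 / 2 = 15 per group, and 15 × 0.20 = 3 Group HPI patients are expected to have events. Treatment on HPI alerts aims to lower that number. Such a count can only be descriptive.

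**The case against.** The strongest reply is that user-rated feasibility with staff support is a legitimate choice for a first pilot, and that the missing data may be captured anyway. Much of this stands.

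- **Data capture.** A reader might infer that adherence goes unrecorded because it is absent from the list of variables in section III. That list covers electronic health record variables only. It also omits the ease ratings, the nurse's answer, nausea and vomiting, all of which are outcomes. The plan refers to data collection forms in the Appendix, and these are not shown. They may hold wear time or signal loss. That would still not make either a listed outcome with an analysis.
- **Staff support.** A reader might infer that the ratings are invalid because research staff run the device. The text does not go that far. Providers are trained on the monitor for unblinded participants, Group HPI care includes reading its screen, and the patient's own rating bears on wearing the cuff. Staff support is a caveat on interpretation, not an error.
- **Expansion.** A reader might infer that the decision to expand rests on the nurse's answer. No such rule exists. The Background states an intent to expand, and III.2.a links continuation to the estimated difference in time-to-treatment.

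None of these points supplies a measure for the two uncovered aims.

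**Conclusion.** The point holds as a mismatch between aims and outcomes. Two of the three aims in III.2.a have no outcome in III.2.c and no analysis in III.4.b, and the feasibility item that is listed has no criterion. The plan can therefore report feasibility without showing usable signal time. The size is structural: no sample size, significance level or stated figure changes, and the documents give no wear-time or failure rate from which to compute an effect. The finding rests on the listed outcomes and analyses alone and does not depend on what the unseen forms contain. It should be corrected before enrolment because it concerns a primary outcome and the correction is cheap.

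**What to change.** **Add to the primary feasibility outcome in III.2.c:** for every randomized patient who starts ELA, minutes of valid ClearSight signal from T0 divided by minutes from T0 to 4 hours or delivery, whichever comes first. Take it from the device record already needed for total time in hypotension, and report it by group. State one T0 for this derivation, because the ELA Protocol ties T0 to the spinal dose and the BP Monitoring Protocol ties it to the test dose.

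**Keep failures in the denominator.** Count patients with device failure or incomplete ClearSight data as low or zero wear time. Say explicitly that the III.2.d exclusions for inability to use the device and for incomplete data do not remove them from this outcome.

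**Keep the nurse and patient ratings alongside**, and say whether nurses of Group CM patients, who are blinded to the output, answer the feasibility question.

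**Optional and descriptive only:** a tally of research-staff interventions per patient, and a count of Group HPI episodes seen at the central monitor (about 3 of 15 patients expected to have events). Both may need new data capture. If the second is not collected, remove central-monitor detection from the aims in III.2.a. A progression threshold is the sponsor's choice.

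**Cost:** revised outcome wording, one export and a short derivation. The downside is that feasibility may look less favourable than under opinion alone.

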**d. Patient inclusion, exclusion, and withdrawal criteria:**

Inclusion

Pregnant  
Receiving epidural labor analgesia (ELA)

Exclusion

Non-reassuring fetal tracing at the time of ELA request  
Contraindications to ELA  
Significant cardiac arrhythmias or aortic regurgitation  
Arrhythmia  
Treatment with antihypertensive medications  
Pre-eclampsia with or without severe features  
Preoperative infection  
Inability to use ClearSight device for any reason.  
Incomplete data  
Sustains unintentional dural puncture during ELA placement

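### Two exclusions with no time limit (ClearSight unusable, data incomplete) can remove randomised patients whose device failed, although ClearSight feasibility is a primary outcome

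*Combined protocol and SAP*

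**What the plan says.** Section III.2.a names ease and feasibility of ClearSight use as the first primary outcome and time to treatment of hypotension as the second. Among the things the pilot is to establish is "the patient adherence to the finger cuff monitors". Section III.2.c gives the feasibility measure: "Feasibility of blood pressure monitoring (yes/no response from assigned nurse regarding patient care".

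Section III.2.d is headed "Patient inclusion, exclusion, and withdrawal criteria", but only an inclusion list and an exclusion list follow. The last three exclusions are "Inability to use ClearSight device for any reason", "Incomplete data" and "Sustains unintentional dural puncture during ELA placement". None carries a time point beyond its own wording.

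Section III.2.e states: "Randomization will be 1:1 and occurs immediately after informed consent and signature for research activities". It also says that consented patients who do not go on to ELA are not randomised. All participants wear both ClearSight and an arm cuff. Under Hypotensive Event Measurement, the endpoint is measured by arm cuff in Group CM and by ClearSight in Group HPI.

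The Statistical Analysis Plan (III.4.b, including the primary and secondary outcome analyses) names no analysis population. It gives no rule for excluded patients or missing data and no denominator for feasibility.

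**The concern.** A feasibility outcome has to count the patients in whom the device did not work. If those patients can be excluded because it did not work, or because the failure left gaps in the record, the outcome is estimated mainly in patients in whom it did work. The 0–10 ease ratings would be exposed to the same selection.

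The second primary outcome is exposed too. A Group CM patient with a ClearSight fault still has a complete arm-cuff record and a treatment time, yet could be dropped. In Group HPI, treatment follows ClearSight output, so removals there may be related to both group and outcome. The pilot is meant to lead to a larger study, and few events are expected: "A total of N=30 patients will be enrolled with a predicted 20% (n=6) experiencing hypotension events of interest".

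**Working it through.** **1. The plan's own figure.** 30 × 0.20 = 6 patients with hypotension. This reproduces.

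**2. Can the exclusions act after randomisation?**

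| Item | When it can be known |
|---|---|
| Incomplete data | Only after data collection |
| Dural puncture at placement | During the procedure, after consent |
| ClearSight unusable | Not stated: before, at or after application |

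So the list is not confined to facts known at screening. III.2.e describes no device check before randomisation. The Pre-ELA Protocol gives a placement rule specific to Group HPI, which suggests that the group is known when the device goes on. III.2.e is inconsistent on whether randomisation comes at consent or only in patients who receive ELA. On either reading, device failures later in the 4-hour monitoring period come after randomisation.

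**3. Effect on feasibility if failures are answered no.** The documents give no failure rate, so the number of failures f is assumed. Also assume that the nurse answers no for every failure and yes for everyone else. With r failures removed, the estimate is (30 − f)/(30 − r). Intervals are exact (Clopper–Pearson) 95%.

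| f | None removed | One third removed | All removed |
|---|---|---|---|
| 3 | 27/30 = 90.0% (73.5–97.9) | 27/29 = 93.1% (77.2–99.2) | 27/27 = 100% (lower limit 87.2) |
| 6 | 24/30 = 80.0% (61.4–92.3) | 24/28 = 85.7% (67.3–96.0) | 24/24 = 100% (lower limit 85.8) |
| 9 | 21/30 = 70.0% (50.6–85.3) | 21/27 = 77.8% (57.7–91.4) | 21/21 = 100% (lower limit 83.9) |

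If only Group HPI answers count (15 patients assumed) and 3 fail, 12/15 = 80.0% (51.9–95.7) becomes 12/12 = 100% (lower limit 73.5).

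**4. Cases where the estimate falls.**
- Failures answered yes: suppose 4 no answers among patients without a failure, and 3 failures answered yes. All 30 kept: 26/30 = 86.7%. The 3 failures removed: 23/27 = 85.2%.
- Successes dropped for incomplete data, starting from 24/30 = 80.0%: removing 3 successes and no failures gives 21/27 = 77.8%; removing 1 failure and 5 successes gives 19/24 = 79.2%.

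**5. Effect on time to treatment.** Assume that 3 of the 6 predicted events fall among 15 Group CM patients and that k of those patients are dropped at random for ClearSight problems. The probability of losing at least one event is 1 − C(12,k)/C(15,k):
- k = 1: 1 − 12/15 = 0.200
- k = 2: 1 − 66/105 = 0.371
- k = 3: 1 − 220/455 = 0.516

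With 2 events among the 15, the three values are 0.133, 0.257 and 0.371. With 4 events they are 0.267, 0.476 and 0.637.

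**The case against.** The best defence is that the device item is a screening rule. It follows seven items that are baseline or screening in kind. III.2.e tells research staff to troubleshoot problems, not to drop the patient, and gives a reason for wanting a working device in everyone: comparing total time in hypotension between groups. That reading is possible, so a reader should not infer that the protocol instructs staff to remove every device failure. However, the wording does not limit the item to screening, and the incomplete-data item cannot be read that way at all. A patient whose finger cuff came off could still be lost through it.

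A reader might also infer that removing failures can only raise the feasibility estimate, or that it would read 100% whatever the true rate. The documents do not support this. The outcome is the nurse's yes/no answer about patient care, not a measure of device function, and a nurse whose patient also wears an arm cuff may answer yes despite a failure. Step 4 shows the estimate falling in that case.

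Three further points stand. No feasibility threshold is stated, so no changed decision about the larger study can be shown. The pilot is not expected to show a significant difference in time to treatment. The data collection forms are not visible in the public document, so whether they record device failures cannot be judged. None of these supplies the missing analysis population.

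**Conclusion.** The gap is real. One exclusion can be applied only after data collection and another has no time limit. With no analysis population defined, the rules as written can remove randomised patients in whom ClearSight failed, and Group CM patients with intact arm-cuff data.

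The direction and size of the effect are not fixed by the documents. If nurses answer no for failed devices, removal inflates feasibility: with 6 assumed failures of 30, from 80% to as much as 100%. If some failures are answered yes, or successes are dropped for missing data, it can move the other way. If nobody is removed, the bias is zero. All failure counts, the 15:15 split, the placement of events and random removal in step 5 are assumptions.

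Should fix, with moderate confidence: a primary outcome is affected and the repair is simple, but the amount of harm cannot be established from the text.

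**What to change.** 1. Delete incomplete data as an exclusion, and limit the ClearSight item to conditions known before randomisation.
2. Report the nurse's yes/no feasibility answer as defined, in all randomised patients who receive ELA, with an exact 95% CI. Show missing answers counted all as yes and then all as no. Beside it, as a separate measure with the same denominator, report by group the proportion in whom ClearSight could not be applied, was abandoned or lost signal. This does not override the nurse's answer.
3. Analyse time to treatment by assigned group in all randomised patients who receive ELA, and do not remove anyone for ClearSight problems. Treatment times remain observable after device loss. The hypotension event in Group HPI may not: it is measured by ClearSight, and the BP Monitoring Protocol states no arm-cuff schedule for that group. State how the event is ascertained after device loss, and show censoring at device loss as a sensitivity analysis.
4. Report every post-randomisation removal by group and reason, with dural puncture and positive test dose on separate rows.
5. Reconcile the two statements in III.2.e on when randomisation occurs.

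The cost is protocol and SAP wording and a little more analysis. The feasibility result may look less favourable. The wording should be settled before data are seen, because patients excluded and not followed cannot be recovered later.

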**e. Protocol specific methods:**

Patients will be screened electronically using the electronic health record upon arrival at the Womancare birth center at UPMC Magee. Patients are eligible if they are pregnant, admitted for labor and delivery, and receiving ELA. If patients are undecided about whether they will receive ELA but are interested in the research, they may be consented and then marked as a "screen failure" if they do not receive ELA. These patients will not be randomized. Patients who receive ELA will be randomized to treatment of hypotension according to conventional monitoring (Group CM) or monitoring by HPI (Group HPI). Randomization will be 1:1 and occurs immediately after informed consent and signature for research activities. Subjects will be informed of their assignment after all research activities and data collection have been completed. Total monitoring time will be 4 hours starting from the initiation of ELA. To enable group comparisons of total time in hypotension, all participants will wear ClearSight and a Conventional Monitoring cuff; Group CM will be blinded to ClearSight output and receive standard care for the treatment of hypotensive events post-epidural-labor analgesia. Group HPI will receive treatment of hypotension according to ClearSight output and specified by the hypotension treatment protocol below.

Clinical research staff who have been trained in ClearSight will apply the device and troubleshoot any problems. Providers will be trained on the monitor, its interpretation, and output, prior to study launch and real time at the time of active study participant enrollment. This training applies only to those participants who will receive non-blinded treatment assignment

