## **ELA Protocol: Combined Spinal Epidural (CSE) Analgesia**

A baseline blood pressure will be recorded immediately prior to the initiation of ELA.

At patient request, an experienced anesthesia provider will perform procedure to place ELA using CSE technique in the sitting position. CSE is chosen due to reliability and rapidity with which hypotension can be predicted within the ELA encounter. A meta-analysis of studies comparing low-dose epidural analgesia with CSE analgesia found no difference in the incidence of hypotension between the two techniques.

The epidural space will be found using loss of resistance to saline. A 25-27g Sprotte needle will be introduced to the subarachnoid space. After confirmation of cerebrospinal fluid (CSF), a spinal dose of 15mcg fentanyl and 2.5mg bupivacaine will be given (this action defines T0 = initiation of CSE). At T0 blood pressure monitoring and data recordings will begin per protocol specified below.

A 19-20g flexible epidural catheter will then be introduced and threaded 5-6cm in the epidural space. Test dose will be delivered through the epidural catheter and will consist of lidocaine 1.5% with epinephrine, 3mL. The anesthesia clinician will declare positive or negative test dose 5 min after administration of test dose. A positive test dose will result in withdrawal from the study.

Maintenance of ELA will be by patient-controlled epidural analgesia using programmed intermittent epidural bolus (PIEB) at our institutional standards: Ropivacaine 0.1% +2mcg/mL fentanyl, 8mL q40min, 8mL demand q8min, maximum hourly volume 24mL. (Smiths CADD®-Solis Infusion System, Infusion Pump, ICU Medical, Dublin, OH). The first PIEB dose is delivered 40 minutes after the initiation of the pump.

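### The protocol gives two incompatible rules for when randomisation happens, and the literal one puts the ELA decision and two eligibility checks after allocation

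*Combined protocol and SAP*

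**What the plan says.** Protocol specific methods (III.2.e) sets the rules in one paragraph. Patients who have not made up their minds about ELA can enter: "they may be consented and then marked as a 'screen failure' if they do not receive ELA". Of those who become screen failures it says: "These patients will not be randomized". It next ties randomisation to actually receiving ELA, and then fixes the time: "Randomization will be 1:1 and occurs immediately after informed consent and signature for research activities". The timing sentence makes no exception for undecided patients.

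The exclusion list (III.2.d) contains items that can become known only after consent. One is "Non-reassuring fetal tracing at the time of ELA request", another is "Inability to use ClearSight device for any reason". The list also has incomplete data and "Sustains unintentional dural puncture during ELA placement". The ELA Protocol adds: "A positive test dose will result in withdrawal from the study". That result is declared 5 minutes after the test dose.

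The Pre-ELA Protocol already contains an instruction for one group only: in Group HPI, both monitors go on the same arm. The Statistical Analysis Plan (III.4.b) names no analysis set. It does not say how patients who are randomised and later excluded or withdrawn are handled, and gives no replacement rule and no allowance for losses.

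**The concern.** An undecided patient who signs the consent form must be randomised at once under the timing sentence. If she later forgoes ELA, she must never have been randomised under the screen-failure rule. Staff cannot know at signature which case she is, so two coordinators could follow different rules in good faith.

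If the timing sentence is the one followed, the ELA decision, the tracing check at ELA request and the ClearSight check all fall after allocation. Patients who fail them become exclusions after randomisation, although they could have been screened out before it. Such exclusions weaken the randomised comparison, use up allocations and can disturb the 1:1 split. They also bear on feasibility, which is a primary outcome: if a patient whose device does not work is simply excluded, evidence the pilot exists to collect is lost.

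**Working it through.** **Which events fall after allocation**

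| Event | When it becomes known | Randomised at consent | Randomised after ELA request and checks, before placement |
|---|---|---|---|
| ELA not received | After consent, for undecided patients | After randomisation | Before, apart from a late change of plan |
| Non-reassuring tracing | At ELA request | After randomisation | Before |
| ClearSight cannot be used | May be known only when applied | May be after randomisation | Before, if a working trace is required first |
| Dural puncture | During placement | After randomisation | After randomisation |
| Positive test dose | After T0 | After randomisation | After randomisation |
| Incomplete data | During or after follow-up | After randomisation | After randomisation |

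The timing affects the first three rows. The last three are unchanged and need an analysis rule instead.

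**Latest workable time.** The Pre-ELA Protocol gives Group HPI its own monitor set-up, so allocation is needed before that set-up is final. Waiting until ELA has been received would be too late. So would the moment before the spinal dose, which is mid-procedure.

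**The plan's own figure.** Inputs from III.2.b: N = 30 and a 20% event rate. Expected patients with events = 30 × 0.20 = 6, as stated. With 1:1 allocation, 30 / 2 = 15 per arm, and 15 × 0.20 = 3 expected per arm.

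**Weight of one loss.** 1 / 15 = 6.7% of an arm.

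**How many might not receive ELA.** The documents give no figure, so this part is assumption. Let u be the share undecided at consent and q the share of those who forgo ELA. If N = 30 counts randomised patients, the loss is 30 × u × q, and expected events are (30 − loss) × 0.20.

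| u | q | Lost | Remaining | Expected events |
|---|---|---|---|---|
| 10% | 10% | 0.3 | 29.7 | 5.94 |
| 25% | 25% | 1.875 | 28.125 | 5.63 |
| 50% | 25% | 3.75 | 26.25 | 5.25 |
| 50% | 50% | 7.5 | 22.5 | 4.5 |

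The result runs from negligible to a quarter of the sample (7.5 / 30), depending wholly on u and q. Losses from tracing and device checks would add to it, and nothing in the documents allows them to be estimated.

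**Fragility with few events.** At a 20% rate, the chance that an arm has no events is 0.8^15 = 3.5% with 15 patients and 0.8^13 = 5.5% with 13.

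**The case against.** The strongest reply is that the paragraph can be read in order. It sets aside undecided patients, then states who is randomised, then when. The specific rule would then govern the general one: immediate randomisation for patients already certain of ELA, deferred for the rest. That reading would remove the conflict. However, the text does not state it, and the timing sentence is unqualified. It would also leave the tracing and device checks after allocation for patients certain of ELA.

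A second reply is that this is a pilot that III.2.a does not expect to show significant differences. That stands, and limits the consequence. But the same section wants the pilot to yield an estimate of potential differences for continuing the study, and with about 6 events one or two exclusions can move that estimate.

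A third reply is that III.2.b speaks of 30 patients enrolled, so losses might be replaced and the 30 still reached. That is possible. The plan does not say what the 30 counts and has no replacement rule, so the reduced totals above are one reading.

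**Conclusion.** The contradiction is real and should be corrected. Its certain part is the wording: two rules that cannot both be applied to an undecided patient. Its consequence is that up to three kinds of exclusion fall after randomisation unnecessarily. The number is unknown. Each loss is 1 of about 15 in an arm, against 6 expected events among 30. The consequence is moderate.

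A reader might infer more, and the documents do not support it:

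- **That early randomisation causes all the later losses.** Dural puncture, positive test dose and incomplete data follow allocation at any workable time.
- **That the early losses are biased because Group HPI staff act on ClearSight output.** The ELA decision and the tracing check come before T0, when recordings under the protocol begin, so hypotension is not yet being treated on that output. Patients learn their assignment only after data collection ends, so their choice of ELA cannot respond to it. The documents do not say when staff learn the allocation. The mechanism fits incomplete data better, and a change of timing does not cure that.
- **That a definite share of the 30 would be lost because of the timing.** Assuming 10% to 30% would give 3 to 9 patients (30 × 0.10 to 30 × 0.30), but such a rate is not in the documents. Applied to all later exclusions, it would include losses that moving randomisation cannot prevent.

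**What to change.** 1. **State one randomisation time.** Replace the wording that places randomisation at consent. Allocation is opened after ELA is requested, eligibility is rechecked and ClearSight is shown to work, but before the group-specific monitor set-up is finalised and before placement begins. Reword the sentence that ties randomisation to receipt of ELA to match, since receipt comes later than this.
2. **Count device failures.** Log every ClearSight failure found before allocation and report it in the feasibility outcome.
3. **Name the analysis set.** Keep all randomised patients in their assigned group for the primary analysis. Report dural puncture, positive test dose and incomplete data by arm, and do not exclude those patients from the analysis. State how a randomised patient who never reaches T0 is counted. This concerns the analysis only and leaves clinical handling of these events untouched.
4. **Define N.** State that N = 30 counts randomised patients.

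The cost is a few sentences in the protocol and the Statistical Analysis Plan. The small practical downside is that allocation must be opened at the bedside shortly before placement.
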